
On February 12, 2016, the treatment phase for the first cohort of randomized participants at the UCD site (5 Leukine treated at the $250\ \text{mcg}/\text{m}^2/\text{day}/\text{SQ}$ and 5 placebo controls) was completed, in addition to 3 randomized participants from the USF site who had completed the trial. The DSMB

reviewed the data for all of these participants and recommended the following changes to the protocol going forward:

- “1) Based on review of the safety data reported to the DSMB, the current study dosing protocol does not present safety concerns and we have no recommended changes to dosing.
- 2) We recommend that the investigators establish specific criteria for terminating subjects from the study due to uncontrolled hypertension, in order to ensure standardized practices across subjects and treatment groups.
- 3) We recommend that with all scheduled DSMB data reviews in the future, the following data be included for review: 1) all vital sign data for each participant, 2) location of injection sites for each treatment and recorded outcomes from injection site review at each treatment visit, and 3) a tabulated list of the dates of treatment for each participant.
- 4) We request a copy at this point in time of the randomization assignment procedure currently being used by the University of Colorado site.
- 5) We recommend against altering the randomization procedure in any manner unless a protocol amendment with justification is approved by the IRB. This recommendation is prompted by the discovery that an investigator requested that the randomization assignment given to an enrolled participant who withdrew from the study be given to the next consecutively enrolled participant (i.e. that the same study drug be assigned to the next participant as had been given to the subject who withdrew).
- 6) The current protocol has no additional blood draws for complete blood count with differential (CBC with diff) beyond treatment day 15. We recommend a protocol change to include an additional CBC with diff on follow up day 90, at the same time as the day 90 scheduled blood draw for biomarkers and comprehensive metabolic panel. We recommend this change for all participants currently enrolled who have not reached day 90 as of April 7, 2016.

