For the indication of Leukine[®] in the acceleration of myeloid recovery in patients undergoing allogeneic BMT from HLA-matched related donors (<http://www.leukine.com/hcp-leukine-in-allogenic-bone-marrow-transplantation>), Leukine[®] was found to be safe and effective in accelerating myeloid engraftment, reducing the incidence of bacteremia and other culture positive infections, and shortening the median duration of hospitalization. In a multi-center, randomized, placebo-controlled, and double-blinded study, a total of 109 patients (53 Leukine[®], 56 placebo) were enrolled to evaluate the safety and efficacy of Leukine[®] for promoting hematopoietic reconstitution following allogeneic BMT. Hypertension was reported in 18 subjects receiving Leukine[®] (34%), and in 18 of the placebo subjects (32%).

On Sanofi's website under Important Safety Information for Leukine[®] (sargramostim), it is stated that "*Leukine[®] should be used with caution and monitored in patients with preexisting fluid retention, pulmonary infiltrates, or congestive heart failure, respiratory symptoms or disease; cardiac symptoms or disease; and renal or hepatic dysfunction.*" Sanofi's website states specifically for Cardiovascular Symptom that "*Occasional transient supraventricular arrhythmia has been reported in uncontrolled studies during Leukine[®] administration, particularly in patients with a previous history of cardiac arrhythmia. However, these arrhythmias have been reversible after discontinuation of Leukine[®]. Leukine[®] should be used with caution in patients with preexisting cardiac disease.*"

Due to safety concerns regarding the potential of cardiac symptoms or disease, the Co-Principal Investigator and/or the DSMB may determine that a trial subject should no longer remain in the trial if there is evidence of uncontrolled hypertension. For an individual who has consented to volunteer for the trial, meets inclusion criteria and is enrolled, then begins the treatment phase of the trial, but who subsequently is determined to exhibit uncontrolled hypertension, the DSMB will be immediately notified, adverse events reporting protocols will be followed, and the following criteria will be used to determine whether the subject needs to be removed from the trial:

Inclusion Screening Criteria for hypertension:

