- Should the potential subject have a screening blood pressure (BP) of more than 150 systolic or 95 diastolic, they will need to be under the care of a primary care provider for management of hypertension.
- The BP will have been well-controlled on a stable regimen for at least two months prior to study entry.
- The screening BP will be no greater than 160 systolic or 95 diastolic. (This limit will apply to all and any BP measurements during the screening process.)

Management Criteria during the treatment phase of the study:

- Should blood pressure rise above 165 systolic or 95 diastolic, the patient will be removed from the study.

- The subject’s hypertensive regimen may be adjusted by the primary care provider during the study as needed.

Sample size considerations:

Due to the well documented safety history of Leukine® ([1], attached as Appendix D) combined with additional patient information from the USF site, we believe that a sample size of 20 patients per research arm is adequate to assess our Primary Endpoint of measuring safety. Although the Moffitt BMT study was not specifically designed to distinguish the cognition of patients receiving GM-CSF plus G-CSF from those receiving G-CSF alone, it was possible to glean conclusions about the cognitive benefit of GM-CSF or G-CSF treatment. The study found highly significant improvement (p<0.01) in the scores of 19 patients receiving GM-CSF plus G-CSF, compared to patients receiving only G-CSF.

A Power analysis showed the following results:

Here is a table of the sample size needed per group with alpha at .20 and power at .60 for independent samples t tests:

Effect size	1 tailed test	2 tailed test
.3 - small	27	53
.5 - medium	10	20
.8 - large	4	8
1.22 – observed from BMT	3	4

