Because of the extensive safety history of Leukine[®] in elderly patients, we do not anticipate any serious safety problems, but we must be vigilant in assessing safety. A review of published adverse events for GM-CSF and the Genzyme Leukine[®] Product Insert and the papers it references will be used to guide the safety monitoring protocol ([38], attached as Appendix D). The greatest safety concern noted with Leukine[®] is excessive leukocytosis. Therefore, as advised by Sanofi/Genzyme Corporation, we will obtain a CBC with differential twice a week during treatment and the dosage will be reduced by half if total ANC rises above 20,000/mm³. In addition, the DSMB described below will monitor laboratory results, the MRI and the cognitive assessments for any indications of toxicity. Following are the abbreviated categories of the National Cancer Institute's (NCI) graded toxicity protocol used by Daud et al., 2008 for assessing safety of Leukine[®] [57], although the latest version of the NCI-CTCAE (Version 4.03) will also be referenced for all AE's (attached as Appendix F):

Anemia
Lymphopenia
Pain
Fever Flu-like symptoms
Arthralgia/myalgia
Injection-site reaction
Fatigue
Abdominal cramps
GERD/indigestion Insomnia
Cough
Sweating

Data and Safety Monitoring Board (DSMB):

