Frequency: An initial meeting of the DSMB, via teleconference or video-conference, will be held before dual enrollment occurs between the two sites in order for the members to review the study protocol and study/participant termination guidelines. Data will be reviewed immediately if a serious adverse event is reported. Otherwise, all data will be reviewed after the first 10 participants (5 Leukine[®]-treatment, 5 placebo control) have completed the initial treatment phase, and again, after each next 10 participants (5 Leukine[®]-treatment, 5 placebo control) have completed the initial treatment phase from both UCD and USF clinical sites. Additionally, review of data will occur in a similar manner as above at 45 and 90 days after treatment for each 10 participants (5 Leukine[®]-treatment, 5 placebo control) from both UCD and USF clinical sites. Furthermore, because this was a multi-center study, serious AE's will be reported immediately to the DSMB, which includes members from both UCD and USF.

Report of Unexpected Problems to the DSMB: The study coordinator will notify the Co-Principal Investigator if there are any unexpected problems. The Co-Principal Investigator will call the **DSMB** when unexpected problems arise that require immediate action.

Criteria for Action:

Specific triggers that will dictate when a specified action (such as reporting or stopping) is required. Any serious adverse event will be reported by the Co-Principal Investigator, [name], to COMIRB using the on-line reporting system. If 2 of 5 subjects experience serious AE's, the FDA will also be notified.

Stopping rules: If serious AE's Grade 3 or 4 occur in 20% of subjects following GM-CSF administration the study will be stopped. For individual subjects, the **DSMB** will discontinue any subject that reaches grade 3 or 4 in any category, or if they decline more than 25% in any of the cognitive tests from baseline. Subjects, are, of course free to withdraw from the study at any time for any or no reason.

Reporting:

Timeframe for reporting: Serious AE's will be reported immediately to the **DSMB** for review and, within 48 hrs (2 business days) to COMIRB. A persistent or significant disability will be reported within 5 business days. The FDA will be notified by written report within one or two weeks if 2 of 5 subjects experience serious AE's.

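### The blood pressure rule takes a subject out of the study, not just off drug, so later safety, imaging and cognitive data are lost in subjects who have had a recorded adverse event

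*Combined protocol and SAP*

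**What the plan says.** **Blood pressure.** The section on removal for cardiovascular events says that the Co-Principal Investigator or the DSMB may decide that a subject "should no longer remain in the trial if there is evidence of uncontrolled hypertension". When this happens during treatment, "the DSMB will be immediately notified, adverse events reporting protocols will be followed". The management criteria then give the rule: "Should blood pressure rise above 165 systolic or 95 diastolic, the patient will be removed from the study". The next bullet lets the primary care provider adjust the antihypertensive regimen. These criteria answer a DSMB recommendation (Trial History, item 2) to "establish specific criteria for terminating subjects from the study due to uncontrolled hypertension".

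**Individual stopping rule.** In the Data Monitoring Plan (Stopping rules), the toxicity trigger is that the DSMB "will discontinue any subject that reaches grade 3 or 4 in any category". A further trigger, on cognition, is worded as follows: "or if they decline more than 25% in any of the cognitive tests from baseline". Whether dosing or participation ends is not stated.

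**Neutrophil count.** In the Data Safety Monitoring Plan the response is to dosing only: "the dosage will be reduced by half if total ANC rises above 20,000" per mm³.

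**Follow-up and analysis.** Study Events and the Study Schedule set out Day 15, 45-day and 90-day visits, with no path for a subject who stops early. The Data Analysis Plan compares safety by injections received. It names no analysis set for the cognitive or imaging outcomes and no method for missing data. The sample size section deals with dropouts by recruiting more subjects.

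**The concern.** A safety threshold that stops dosing is sound, and this one is not disputed. The difficulty is that the rule also ends observation. The trial's first aim is tolerability and safety, and its MRIs are there partly to look for vasogenic edema and microhemorrhage. A subject whose blood pressure crosses the limit has just had an event that the protocol treats as reportable. If that subject leaves the study, later adverse event reviews and all post-treatment imaging are missing because of a safety event. Missing data of this kind cannot be treated as unrelated to outcome.

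**Working it through.** The plan gives no figure for removals or lost visits, so there is none to reproduce. The loss follows from the Study Schedule.

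**Inputs (Study Schedule and Study Events).** Adverse events are reviewed at 15 injection visits and 2 follow-up visits, so 15 + 2 = 17 reviews. Post-baseline MRI is at Day 15 and 45 days (2), follow-up PET at 45 days (1), and post-baseline cognitive testing at Day 15, 45 days and 90 days (3). Day 15 is the fifteenth injection visit.

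**Loss from removal at injection visit k, with k below 15.** The review at visit k is done, so the number undone is 17 − k. Every post-baseline MRI, PET and cognitive battery falls at Day 15 or later, so all are lost whatever the value of k.

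| Removed at visit | Adverse event reviews undone | MRIs lost | PET lost | Cognitive batteries lost |
|---|---|---|---|---|
| 4 | 17 − 4 = 13 | 2 of 2 | 1 of 1 | 3 of 3 |
| 8 | 17 − 8 = 9 | 2 of 2 | 1 of 1 | 3 of 3 |
| 12 | 17 − 12 = 5 | 2 of 2 | 1 of 1 | 3 of 3 |

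**How often could it happen?** No crossing rate is given. The margins are narrow: screening admits up to 160 systolic or 95 diastolic and removal is above 165 or 95, so there are 5 mmHg of systolic room and none of diastolic. No repeat reading is required. For illustration only, suppose each of the 15 treatment-visit readings crosses independently with probability q. The chance of at least one crossing is 1 − (1 − q)^15, which is 7% for q = 0.5%, 14% for q = 1% and 26% for q = 2%. Readings within one person are correlated, so for a given q the true share would be lower.

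**Reach.** The update on the current amendment counts 30 participants as having completed (the last with one follow-up visit to go) against a target of 40. Retained visits can therefore help about 40 − 30 = 10 subjects. On the illustrative rates that is 10 × 0.07 to 10 × 0.26, or about 0.7 to 2.6 subjects. A rule on analysis and reporting would cover everyone randomised.

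**Individual stopping rule.** The first post-baseline cognitive test is at the last injection visit, so the cognitive trigger can spare at most one dose. Its other purpose is monitoring: the DSMB "will monitor laboratory results, the MRI and the cognitive assessments for any indications of toxicity". Data can be lost only if *discontinue* means leaving the study. Routine DSMB review is by batches of 10. The first UCD cohort finished treatment on 12 February 2016 and the DSMB report is dated 6 April 2016, 17 + 31 + 6 = 54 days later. That is after the 45-day visit, and 90 − 54 = 36 days before the 90-day visit of a subject treated to the last day. On that one example, mainly the 90-day visit is exposed. For grade 3 or 4 toxicity the protocol reports no study-related serious adverse event so far, so few removals are to be expected by that route.

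**The case against.** **The event is captured.** This stands. Adverse event reporting applies, and the section on reporting mechanisms requires the outcome of the event. A reader might infer that removed subjects drop out of the primary comparison. The documents do not say so: the safety groups are defined by injections received, and a dosed subject belongs to them.

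**Removal may be discretionary.** The introductory text says that removal may be decided, and the regimen can be adjusted. But the criterion itself is worded as automatic, and neither provision keeps a removed subject in imaging or follow-up.

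**The DSMB asked for termination criteria.** It did, and the sponsor adopted its wording. Changing the consequence therefore needs the DSMB's agreement. The threshold need not change.

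**There is no sign of removal differing by arm.** This also stands. Hypertension in the cited Leukine trials was 25% against 32% on placebo, and 34% against 32%. A reader might infer a bias between arms or a link between blood pressure and MRI findings; the documents support neither.

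**Confidence limits for MRI events.** One might argue that unscanned subjects loosen the zero-event upper limit, from 1 − 0.05^(1/20) = 13.9% with 20 scanned to 16.2% with 17. This presumes that removed subjects are not replaced, whereas the plan over-recruits for dropouts. With replacement 20 are scanned and the limit stays at 13.9%. The concern that remains is which subjects are scanned, not how many.

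**The withdrawn participant in DSMB item 5.** This might be read as the rule in operation. No reason for withdrawal is given, and the case predates the rule.

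**The neutrophil rule is not a precedent for staying on study off drug**, since that subject continues at half dose. It shows only that the protocol can act on dosing without ending participation.

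**Conclusion.** The point holds for the blood pressure rule. Followed literally before Day 15, it ends all later adverse event reviews, MRI, PET and cognitive testing for the subject, and so removes safety data selectively from people with a recorded adverse event. The loss per removed subject is exact from the schedule. The number of such subjects is unknown, and about 10 of 40 could still benefit from retained visits.

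For the individual stopping rule this is mainly a request for clarity. A reader might infer a material bias in the late cognitive comparison from losing those who decline. That would need the study-exit reading, removals taking effect before the late visits, and assumed values for the trigger in SD units and the correlation between visits, none of which the documents supply. The effect is probably small, and no bias figure is claimed here.

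The conclusion rests on the protocol text. The consent form was not available and could describe follow-up after removal.

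**What to change.** In the blood pressure management criteria and in the individual stopping rule, state that:

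- meeting a trigger stops study drug only;
- the subject keeps the Day 15, 45-day and 90-day safety, imaging and cognitive visits, unless consent is withdrawn or the investigator or DSMB judges a procedure unsafe or not warranted;
- the subject is analysed in the randomised arm.

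The second PET is an example of a procedure that might be waived: it adds 2.9 + 0.6 = 3.5 mSv, perhaps after only a few doses. Report the number meeting each trigger by arm for all randomised subjects, including any already removed. Leave the blood pressure and cognitive thresholds unchanged.

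The cost is a protocol amendment with DSMB and IRB agreement, and a few already scheduled visits for subjects off drug among the roughly 10 still to be enrolled.

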
PRELIMINARY CLINICAL RESULTS:

Moffitt Cancer Center:

Together with [name] of the Moffitt Cancer Center, we performed a retrospective analysis of the data that was gathered from a study assessing cognition in Bone Marrow Transplant patients, who acquire cognitive deficits from the chemotherapy or irradiation procedures ([3], attached as Appendix C;[33]). Their cognitive function was measured

before treatments and then 6 months and 12 months after transplant and associated treatment, with a combination of either GM-CSF plus G-CSF or G-CSF alone. The neurological measures used included some of the cognitive measures that are used routinely to assess AD patients.

Total neuropsychological performance z scores (TNP) were calculated by summarizing the cognitive domains of memory, executive functioning (i.e., complex cognition), and attention. Scores indicate change in TNP from pre-transplant baseline. Kruskal-Wallis one-way analyses of variance were conducted at six months and 12 months after baseline assessment and hematopoietic cell transplantation (HCT), using all available data to compare between-group changes in TNP by receipt of GM-CSF. Wilcoxon signed rank tests were conducted using all available data to examine within-group changes in TNP by receipt of GM-CSF. Despite a high level of education (average of 13.89 years), the subjects displayed a statistically significant cognitive deficit at baseline.

The preliminary results show that patients who received GM-CSF plus G-CSF improved their cognitive functions (neuro minus motor features) between base line and six months, whereas subjects receiving only G-CSF did not improve (Figure 4 below). This result validates in humans that GM-CSF can improve cognition in an at-risk population using the standard recommended, FDA-approved dosage that we propose to also use in this protocol. This human study also showed that a small number (less than 20) of patients only receiving part GM-CSF at the standard FDA-approved dose was sufficient to reveal that GM-CSF led to improved cognitive measures 6 months after HCT and CSF treatment, compared to the much larger group receiving G-CSF alone.

University of South Florida:

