Before initiation of the current trial at the UCD site, fourteen participants enrolled in a preliminary study at USF. Of these 14 participants, 9 completed the entire study, including both follow-up visits; and the other 5 completed all treatment visits and at least one of the follow-up visits. Also, 3 of the 14 participants may have received the full Leukine® dose, but this number cannot be definite due to blinding of the study team at USF. Finally, the only AE's reported include injection site reactions seen in 6 patients (redness, raised, itching, bruising). No serious AE's were reported in these 14 participants.

The current trial (COMIRB #12-1273) was originally approved as a multi-site trial with recruitment efforts again, at USF, in Tampa, FL. USF's recruitment yielded 5 subjects who were enrolled into the current trial. Two of these subjects were screen failures and three completed the trial at USF. USF's last subject officially completed the trial on June 12th, 2015. However, due to USF's low recruitment, the decision was made to amend the protocol and close USF as a site. This amendment was approved by COMIRB on July 25th, 2016. Since the closure of the USF site, the research team at UCD has received all pertinent study data and study samples via secure HIPAA compliant practices.

[figure not shown]

Figure 4. Total Neuropsychological Performance in Hematopoietic Cell Transplant (HCT) Recipients Receiving GM-CSF+G-CSF versus G-CSF Only.

The GM-CSF+G-CSF group performed significantly better at 6 months post-HCT ($p=.04$), but there were no group differences at 12 months post-HCT ($p=.24$). The GM-CSF+G-CSF group improved significantly from baseline to 6 months post-HCT ($p=.01$) and from baseline to 12 months post-HCT ($p<.01$). The G-CSF group demonstrated no change from baseline to 6 months post-HCT ($p=.33$) but significant improvement from baseline to 12 months post-HCT ($p<.01$). Note: No patients received GM-CSF only. (GM-CSF: Granulocyte-Macrophage Colony-Stimulating Factor; G-CSF: Granulocyte Colony-Stimulating Factor)

EXPERIMENTAL DESIGN AND METHODS:

Recruitment:

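### The p<0.01 cited for GM-CSF plus G-CSF versus G-CSF alone conflicts with the Figure 4 caption (p=.04 and p=.24), and the 1.22 effect size drawn from that study has no stated derivation

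*Combined protocol and SAP*

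**What the plan says.** All references are to the combined protocol and SAP.

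- **Sample size considerations** reports from the BMT study "highly significant improvement (p<0.01) in the scores of 19 patients receiving GM-CSF plus G-CSF, compared to patients receiving only G-CSF". Its power table, for independent-samples t tests at alpha .20 and power .60, ends with a row labelled "1.22 – observed from BMT", giving 3 per group one-tailed and 4 two-tailed. The text below the table describes this effect as very large, uses it as the reference for choosing the number of AD subjects, says three or four would suffice, and moves by a *therefore* to the 40 proposed in the November 15, 2013 protocol.
- The same section gives a second rationale: "a sample size of 20 patients per research arm is adequate to assess our Primary Endpoint of measuring safety".
- **Dosage** repeats p<0.01 for GM-CSF plus G-CSF against G-CSF alone, identifies it as the result in Preliminary Clinical Results, and says it allowed the power calculation.
- **Preliminary Clinical Results** describes the between-group test: "Kruskal-Wallis one-way analyses of variance were conducted at six months and 12 months after baseline assessment". The comparison was with a group described only as larger: "compared to the much larger group receiving G-CSF alone".
- The **Figure 4 caption** says the GM-CSF plus G-CSF group "performed significantly better at 6 months post-HCT ($p=.04$), but there were no group differences at 12 months post-HCT ($p=.24". Within groups it reports p=.01 (6 months) and p<.01 (12 months) for GM-CSF plus G-CSF, and p=.33 and p<.01 for G-CSF alone.

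**The concern.** The p<0.01 is presented as a comparison between groups, but the section it is attributed to contains no such between-group result. The only p<.01 values there are changes from baseline to 12 months, and the comparator group has one too, so they do not separate the treatments.

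The same study supplies the 1.22. No score, visit, means, standard deviations or formula is given, nor whether the effect is between or within groups. An independent-samples t test needs a between-group effect. If 1.22 is that, on the Figure 4 score, it does not fit the caption; if it is within-group, it is the wrong input for the table.

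At stake is how a cognitive result will be read. At d=1.22, 20 per arm has about 99% power at two-sided alpha .20. A reader who accepts that figure would treat a null cognitive finding as far more informative than it is.

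**Working it through.** **Inputs from the protocol.** Alpha .20, power .60 and d=1.22 (power table); 19 GM-CSF patients (Sample size considerations); between-group p=.04 and p=.24 (Figure 4 caption); 20 per arm.

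**Assumptions.** The comparator size n2 is not given, so 40 to 1000 is used. All 19 GM-CSF patients are taken as evaluable at each visit, p values as two-sided, and the t distribution as an approximation to the rank test.

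**1. The plan's own table.** Per-group n from the noncentral t distribution:

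| d | Stated (1-tailed / 2-tailed) | Recomputed |
|---|---|---|
| 0.3 | 27 / 53 | 27 / 53 |
| 0.5 | 10 / 20 | 10 / 20 |
| 0.8 | 4 / 8 | 4 / 8 |
| 1.22 | 3 / 4 | 2 / 4 |

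Seven of eight cells match, and the one-patient difference is immaterial. The method is sound; the question is the input to the last row.

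**2. The p value that d=1.22 would give.** t = 1.22 / √(1/19 + 1/n2), with 17 + n2 degrees of freedom.

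- n2=40: t = 1.22/0.2786 = 4.38, p = 0.00005
- n2=100: t = 1.22/0.2503 = 4.87, p = 0.0000035
- n2=1000: t = 1.22/0.2316 = 5.27, p = 0.0000002

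With the Kruskal-Wallis test the protocol names, 3000 simulated normal datasets with the observed d fixed at 1.22 gave a median p of about 0.00015 (n2=40) and 0.00003 (n2=80). None reached .01. For d=1.22 to give p near .04, the GM-CSF group would have to be about 3 patients (n2=40: 0.048; n2=100: 0.040).

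**3. The d that the caption's p values imply.** d = t(1−p/2, 17+n2) × √(1/19 + 1/n2). For example, p=.04 with n2=40 gives 2.102 × 0.2786 = 0.586. The per-group n is at the table's alpha .20 and power .60; the last two columns are two-tailed power at alpha .20.

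| p | n2 | Implied d | n per group, 1-tailed / 2-tailed | Power, 4 per group | Power, 20 per group |
|---|---|---|---|---|---|
| .04 | 40 | 0.586 | 8 / 15 | 32% | 71% |
| .04 | 100 | 0.520 | 10 / 18 | 30% | 64% |
| .04 | 200 | 0.496 | 10 / 20 | 29% | 61% |
| .04 | 1000 | 0.476 | 11 / 22 | 28% | 58% |
| .24 | 40 | 0.331 | 23 / 44 | 24% | 41% |
| .24 | 100 | 0.296 | 28 / 54 | 23% | 37% |
| .24 | 200 | 0.283 | 31 / 59 | 23% | 36% |
| .24 | 1000 | 0.272 | 33 / 64 | 23% | 35% |

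**4. Sensitivity to fewer evaluable patients.** With only 10 GM-CSF patients analysed, d=1.22 still gives p of 0.0012 to 0.00013. p=.04 then implies d of 0.75 to 0.65 (9 to 12 per group two-tailed), and p=.24 implies 0.42 to 0.37 (27 to 34).

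**5. The within-group reading.** If 1.22 is the mean change divided by its standard deviation, then t = 1.22 × √19 = 5.32 and p = 0.00005. That is compatible with the caption's p<.01 at 12 months but not with its p=.01 at 6 months.

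**6. Power at the planned size.** For 20 per arm at unadjusted two-sided alpha .20, power is 61% at d=0.5 and 38% at d=0.3.

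**The case against.** The 1.22 half is conditional. The source study is attached to the protocol as Appendix C, which was not available here, and may contain a derivation or a between-group p<0.01 on another score. This stands. The p-value mismatch is firm on the text; the conflict over 1.22 depends on what that number is.

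The Sample size wording might be read as attaching p<0.01 to improvement from baseline. The Dosage section rules this out for its own statement, which is a direct comparison of the two regimens and refers back to the section containing Figure 4.

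The consequence is also limited. The trial is a pilot, cognition is secondary, and 20 per arm is justified on safety. Three or four subjects cannot lead to 40, and that sentence describes what an earlier protocol proposed. With the effect implied by p=.04, 20 per arm has 58% to 71% power, around the table's own 60% target. The table already shows 20 per group for a medium effect and 53 for a small one. All this stands, and it is why no change in enrolment is asked for. It does not rescue the statement that three or four subjects suffice, which remains in the current text.

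The p=.24 scenario is the weaker benchmark: it is a 12-month result, while this trial's last visit is about three months after treatment. The 6-month figure is the nearer comparison, and it still needs 15 to 22 per group two-tailed rather than 4.

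**Conclusion.** The concern holds. Two sections cite a between-group p<0.01 that the section they rely on does not contain. Which statement matches the source study cannot be settled from the documents reviewed.

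The 1.22 lacks a derivation. As a between-group effect on the Figure 4 score it cannot be squared with the caption under any comparator size from 40 to 1000, whether 19 or 10 GM-CSF patients were analysed. On the caption's 6-month result, the two-tailed requirement is roughly four to five times the stated 4 per group (15/4 ≈ 3.8; 22/4 = 5.5), and 4 per group would have about 28% to 32% power instead of 60%.

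This should be fixed. It affects the stated power for cognition, not the primary safety design.

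**What to change.** 1. Check the p<0.01 statements, the Figure 4 caption and the 1.22 against the source study in Appendix C.
2. Unless that source documents a between-group p<0.01, replace the statement in Sample size considerations and in Dosage with: *On the Figure 4 score, GM-CSF plus G-CSF was superior to G-CSF alone at 6 months (between-group p=.04) but not at 12 months (p=.24).*
3. Unless a between-group derivation of 1.22 is documented (measure, visit, means, SD, n per group), delete the 1.22 row, the sentence on the size of the BMT effect and the sentence on three or four subjects. Keep the record of what the November 15, 2013 protocol proposed, and add: *The earlier power rationale is withdrawn; the current 20 per arm rests on the safety justification above.* If the sponsor prefers another basis for the 40, it should state that instead.
4. In either case, add below the table: *With 20 per arm, power for a single cognitive comparison is about 61% at d=0.5 and 38% at d=0.3 at unadjusted two-sided alpha .20, and lower after the Bonferroni correction.* The table shows the 20 for d=0.5 but not the 38%, nor the effect of the correction promised in the Data Analysis Plan. Give no Bonferroni power figures until the analysis alpha and the number of comparisons are stated.

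The cost is a source check and some rewording, with a less favourable power statement for cognition. Enrolment, endpoints and tests do not change.
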